Secondary Aim: Examine the influence of menthol flavor on the effects of nicotine (freebase vs salt) stimulation, craving reduction, and alleviation of nicotine withdrawal. Participants will rate nicotine withdrawal and stimulation using the Revised DEQ and cigarette craving using the gLMS.

Exploratory Aim: Examine nicotine delivery following exposure to nicotine salt vs freebase nicotine exposure in combination with flavors (tobacco or menthol) by measuring saliva nicotine levels 5 min prior and 5, 15, 30, 45, and 55 minutes after nicotine and flavor exposure via e-cigarettes

K01 metabolism study

Eighty-Five African Americans (43 F, 42 M) who smoke and have experience with e-cigarettes will participate in a double-blind, randomized, cross-over study across two experimental sessions. Following overnight abstinence from combustible tobacco products (CO≤10 ppm), participants will be randomly assigned to receive an e-cigarette with menthol flavor or control tobacco flavor (both in a concentration of 5% nicotine) on two separate days. Each session will consist of 1 puffing bout (10 puffs, 3 sec each puff, 30 sec puff interval) followed by 2 hours of abstinence, then 60 minutes of ad libitum e-cigarette use. The specific aims are:

Aim 1: Investigate the relationship of menthol flavor (vs tobacco flavor) and nicotine metabolite ratio (NMR) on nicotine pharmacokinetics and subjective effects during directed e-cigarette administration in African Americans who smoke. We hypothesize that during the menthol exposure session participants will have higher plasma nicotine levels compared to the tobacco flavor exposure session. We hypothesize that NMR is negatively associated with nicotine plasma levels during the tobacco flavor exposure sessions. Lastly, we hypothesize that participants will have a larger reduction of cigarette craving in the menthol compared to tobacco session. Primary outcomes: plasma nicotine boost, nicotine area under the curve. Secondary outcome: cigarette craving. Exploratory outcomes: other subjective effects such as liking of e-cig taste. Gender differences will be explored for all outcomes.

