Aim 2: Elucidate the relationship between menthol flavor (vs tobacco flavor) and NMR on nicotine pharmacokinetics and subjective effects during e-cigarette ad libitum use in African Americans who smoke. We hypothesize that participants will take more puffs during the menthol session compared to the tobacco session. Additionally, we hypothesize that participants will titrate their nicotine intake and have similar nicotine plasma levels for both flavor exposure sessions. Furthermore,

we hypothesize that NMR will be positively associated with nicotine delivery (amount of e-liquid used x nicotine e-liquid concentration) for both flavor sessions. Lastly, we hypothesize that participants will have a larger reduction of cigarette craving in the menthol compared to tobacco session. Primary outcomes: plasma nicotine boost, nicotine area under the curve. Secondary outcomes: measure of nicotine delivered to participant and cigarette craving. Exploratory outcomes: number of puffs and subjective effects. Gender differences will be explored for all outcomes.

2. **Probable Duration of Project:** State the expected duration of the project, including all follow-up and data analysis activities.

2 years

TCORS Menthol Pilot Study

Study	Quarter 1	Quarter 2	Quarter 3	Quarter 4
2 experiment sessions	7 completers	7 completers	8 completers Analyze results.	8 completers Analyze results. Present at conference. Publish

K01 Metabolism Study

I anticipate completing both phases of the study by the end of this 5-year K01 award (funded Sept 2020). I anticipate completing 21 participants per year.

3. **Background:** Describe the background information that led to the plan for this project. Provide references to support the expectation of obtaining useful scientific data.

TCORS Menthol Pilot Study

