African Americans are disproportionately burdened with tobacco-related health diseases compared to other racial groups in the US^{23,24}. African Americans who smoke are more likely to develop lung cancer compared to smokers of other ethnic/racial groups^{25,26}. These health disparities exist even though African Americans are more likely to be light smokers (smoke less than 10 cigarettes per day)^{27,28} and less likely to be daily smokers^{29,30}. African Americans also take in more nicotine when smoking compared to White people who smoke³¹. The more intense smoking by African Americans may be related to the observation that 80% of African Americans who smoke are menthol smokers^{5,32}. Menthol has cooling and analgesic properties via the transient receptor potential channels^{33,34}, which may reduce irritation from tobacco smoke and nicotine^{18,35}. **Menthol cigarettes pose a greater public health risk than non-menthol cigarettes because those who use menthol cigarettes have higher nicotine dependence^{5,36-38} and decreased success in quitting smoking^{37,39}.**

It is important to understand the role of menthol flavor in nicotine dependence in African Americans. Nicotine, a compound found in tobacco products, activates nicotinic acetylcholine receptors in the mesolimbic pathway to induce rewarding and reinforcing properties⁴⁰. Constituents of tobacco products that have an influence on nicotine levels may influence dependence and addiction of tobacco products. Preclinical studies suggest that menthol inhibits nicotine metabolism⁴¹ by inhibiting the enzyme primarily responsible for the metabolism of nicotine through oxidation, CYP2A6⁴². Additionally, studies have also shown that African Americans who smoke have a slower nicotine metabolism than White people who smoke^{31,43,44}. African Americans who smoke have been shown to have slower oxidative metabolism of nicotine and slower N-glucuronidation than White people who smoke⁴⁵. However, since 80% of African Americans who smoke, smoke menthol cigarettes, it is unclear if the effect on nicotine metabolism in African Americans is the result of menthol exposure. Furthermore, there are few studies that have investigated the differential impact of menthol on nicotine metabolism within the African American population. Additionally, It has been shown that females who smoke are more likely to smoke menthol cigarettes compared to men, however gender differences within Black people who smoke is understudied⁴⁶.

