24. Urine drug and pregnancy tests: Urine drug screen will assess recent drug use at intake for both studies. If participants test positive for any drugs except marijuana and drugs they are not prescribed at the in-person intake appointment, they will not be paid for the visit and will have the opportunity to reschedule this appointment one time. Urine drug screen assesses benzodiazepines, marijuana, methadone, cocaine, methamphetamine, morphine, MDMA, oxycodone, barbiturates, buprenorphine, amphetamine phencyclidine, methadone metabolites,

tricyclic antidepressants and propoxyphene. We will administer pregnancy tests to all female participants at baseline and every vaping session appointment while they are enrolled in the study. In addition, female enrollees will be verbally asked about their pregnancy risk (such as unprotected sex or a missed menstrual period).

25. Plasma nicotine levels for K01 metabolism study will be assessed using blood samples obtained at baseline and 5, 15, 30, 45, 60 minutes after nicotine exposure during the directed e-cigarette portion and plasma nicotine levels will be assessed using blood samples obtained at baseline and 15, 30, 60 minutes after nicotine exposure during ad-lib session. 60 ml of blood will be drawn at each e-cigarette exposure through insertion of an intravenous catheter during e-cigarette directed administration session (total of 120ml for all laboratory session in study or 8 tablespoons) which is below the IRB guidelines of 450 ml within eight research weeks. We will recommend participants wait at least 4 weeks to donate blood. We will then calculate the nicotine boost and the area under the curve. These levels will be determined using LC/MS techniques through the Yale TCORS Lab and Analytical Core.
26. Amount of nicotine delivered to participants will be assessed for K01 metabolism study. The amount of e-liquid in pods will be measured before and after the ad-lib e-cigarette exposure period. We will then multiply the amount of e-liquid used by the nicotine concentration of the e-liquid (5%) to calculate the amount of nicotine delivered to the participants⁶².

5. Genetic Testing N/A

6. **Subject Population:** Provide a detailed description of the types of human subjects who will be recruited into this study.

TCORS menthol pilot study

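### K01 Aim 2 predicts more menthol puffs together with titration to similar plasma nicotine. Given Aim 1 these pull in opposite directions unless menthol puffs are smaller, and the plan does not prespecify what a titration conclusion needs.

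*Combined protocol and SAP*

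**What the plan says.** Section I.1 (Statement of Purpose, K01 metabolism study) sets three predictions about flavor and nicotine.

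- Aim 1, a directed bout of 10 three-second puffs that is identical in both sessions: "We hypothesize that during the menthol exposure session participants will have higher plasma nicotine levels compared to the tobacco flavor exposure session".
- Aim 2, 60 minutes of ad-lib use of the same pods, later in the same session: "We hypothesize that participants will take more puffs during the menthol session compared to the tobacco session".
- Aim 2 again: "we hypothesize that participants will titrate their nicotine intake and have similar nicotine plasma levels for both flavor exposure sessions".

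Aim 2 adds a prediction about metabolism: "we hypothesize that NMR will be positively associated with nicotine delivery (amount of e-liquid used x nicotine e-liquid concentration) for both flavor sessions". Its primary outcomes are ad-lib plasma nicotine boost and area under the curve. The others are ranked thus: "Secondary outcomes: measure of nicotine delivered to participant and cigarette craving. Exploratory outcomes: number of puffs and subjective effects". No flavor direction is stated for nicotine delivered.

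Under Assessments in Section I.4, item 22 lists number of puffs and time to first puff, coded from video. Puff duration and volume are not listed. Item 26 says "The amount of e-liquid in pods will be measured before and after the ad-lib e-cigarette exposure period", and the amount used is multiplied by the nicotine concentration.

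Section I.13 (Statistical Considerations) gives one mixed model for both aims, with NMR, time, flavor, their interactions and sex. Power is stated for a correlation of 0.30 and for a within-subject difference of d = 0.32. There is no equivalence margin, no rule for calling levels similar, and no analysis that reads the two aims together.

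**The concern.** Both pods carry the same nicotine concentration. If a standard menthol puff gives a higher plasma level, a participant who titrates to the same level must take less: fewer puffs, smaller puffs, or both. The puff-count prediction points the other way. Smaller menthol puffs could reconcile the three statements, but the plan does not say so, and no listed outcome shows nicotine used per puff.

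The second difficulty is inferential. Titration is tied to similar plasma levels, yet levels could also be similar because flavor altered neither yield nor puffing. The planned model tests for a difference. If a null result on Aim 2's primary outcomes were reported as titration, a trial with no flavor effect at all could appear to confirm it.

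**Working it through.** **The plan's own figures.** Correlation of 0.30, two-sided 5%, 80% power, by Fisher z: n = ((1.960 + 0.842)/atanh(0.30))² + 3 = 84.9, so 85. This reproduces. Paired d = 0.32 at N = 85 by noncentral t gives 83.1% power, against the stated 80%. The statement is slightly conservative and not in error. Both figures concern detecting an effect, not showing similarity.

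**Coherence of the three predictions.** Write the ad-lib plasma ratio (menthol/tobacco) as r × p × v. Here r is the ratio of level per standard puff (Aim 1 says r > 1), p the ratio of puff counts (Aim 2 says p > 1) and v the ratio of puff sizes. Titration to similar levels means r × p × v ≈ 1. The documents give no values, so r and p below are assumptions, as is proportionality of level to puffs and puff size.

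| r | p for equal plasma, v = 1 (1/r) | plasma ratio at p = 1.10 / 1.20 / 1.30, v = 1 | v for equal plasma at p = 1.10 / 1.20 / 1.30 |
|---|---|---|---|
| 1.05 | 0.95 | 1.16 / 1.26 / 1.37 | 0.87 / 0.79 / 0.73 |
| 1.10 | 0.91 | 1.21 / 1.32 / 1.43 | 0.83 / 0.76 / 0.70 |
| 1.20 | 0.83 | 1.32 / 1.44 / 1.56 | 0.76 / 0.69 / 0.64 |
| 1.30 | 0.77 | 1.43 / 1.56 / 1.69 | 0.70 / 0.64 / 0.59 |

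With equal puff size, similar plasma needs 5% to 23% fewer menthol puffs. With 10% to 30% more menthol puffs, plasma is 16% to 69% higher unless puffs are 13% to 41% smaller. The direction does not depend on whether r > 1 comes from delivery or from slower clearance.

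**What similar plasma can mean.** If r = 1 and p = v = 1, the ratio is 1 with no titration. If r > 1 and p = v = 1, the ratio is r, so levels differ without titration. Similar plasma is therefore informative only alongside evidence that r > 1.

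**What a null flavor test can mean.** Chance of a non-significant paired test at N = 85:

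- true d = 0: 95%
- d = 0.10: 85%
- d = 0.20: 55%
- d = 0.32: 17%

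**What a margin would offer.** For two one-sided tests at 5% each with a true difference of zero, power ≈ 2Φ(margin × √85 − 1.663) − 1. At a margin of d = 0.32 this is 2Φ(2.950 − 1.663) − 1 ≈ 0.80, and simulation gives 80%. At margins of 0.20, 0.25 and 0.40, simulation gives 15%, 48% and 96%. The half-width of the 90% interval is 1.663/√85 = 0.18 SD.

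**A within-person regression as an alternative rule.** One could regress the log ratio of ad-lib nicotine used on the log ratio of the directed-bout rise. Assume a true-yield SD of 0.25, 0.40 as measured, a residual SD of 0.50 and full titration. Then correlation = −0.0625/(0.40 × √(0.0625 + 0.25)) = −0.28, and Fisher-z power at 85 is about 74%. With the same measurement error (variance 0.40² − 0.25² = 0.0975) and residual, a true-yield SD of 0.10 gives about 8%. Half titration gives 28%, and a correlation of 0.13 between the errors gives about 41%. If menthol raised yield 20% in everyone and everyone cut intake 17%, the expected slope would be zero and titration would be missed almost always.

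**The case against.** The strongest reply is that the design carries more information than the hypotheses suggest. Both aims use the same people, pods and sessions, so a clear directed-bout gap that vanishes ad lib is some evidence of titration. Nicotine delivered is already a secondary outcome and reflects puff size as well as count, and nicotine per puff is the ratio of two listed measures. The NMR hypothesis also bears on compensation, though for metabolism rather than flavor. Puff count is only exploratory, and ad-lib puff size is free, so the predictions are not strictly contradictory. All of this stands, and it limits the point to what is prespecified.

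A reader might go further and infer any of the following. The documents do not support them.

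- That the planned comparisons cannot support or refute titration. Higher ad-lib plasma with menthol would count against the hypothesis, and the flavor test has about 83% power at d = 0.32.
- That similar levels would occur without titration whatever happens in Aim 1. If Aim 1 holds and puffing is equal, levels differ.
- That the puff comparison is one-sided, or that fewer puffs would be read as titration. The hypothesis is directional, but no one-sided test appears, and fewer puffs would contradict it.
- That menthol puffs would have to be very much smaller. At the low end of the assumed ranges, 13% smaller suffices.

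**Conclusion.** The point holds in a limited form. Given Aim 1, titration to similar levels implies fewer or smaller menthol puffs. The puff-count hypothesis therefore points the other way unless menthol puffs are smaller, and the plan neither says this nor makes nicotine per puff an outcome. Similar plasma or a non-significant flavor term does not by itself show titration, and the plan gives no margin or joint pattern that would. The raw data for a better answer are planned; the prespecification is missing.

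The direction follows from the protocol's own hypotheses. The sizes (5% to 23% fewer puffs, or 13% to 41% smaller) rest on assumed values of r and p and on proportionality. The error rates rest on a paired comparison of 85 completers. Aim 1 and the stated power are unaffected. What changes is what Aim 2 may conclude from its primary outcomes.

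**What to change.** 1. In Section I.1, reconcile the puff-count hypothesis with Aim 1 and the titration hypothesis. If smaller menthol puffs are expected, say so.
2. Add ad-lib nicotine used per puff (the item 26 amount divided by video-coded puffs) by flavor as an exploratory outcome beside nicotine delivered.
3. In Section I.13, state that titration will not be inferred from similar plasma or a non-significant flavor test alone. Conclude it only if the directed bout shows higher plasma nicotine with menthol, ad-lib nicotine delivered is lower with menthol, and the confidence interval for the ad-lib plasma flavor difference (90% for two one-sided 5% tests) lies within a prespecified margin. The margin is the investigators' choice; d = 0.32 would have about 80% power at N = 85 if the true difference is zero.
4. The within-person regression may be reported as exploratory. It should not be the decision rule, because it misses uniform titration and its power depends on assumed SDs.

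The cost is wording and slightly more analysis, with no new measurements. The downside is a titration conclusion that is harder to reach: all three conditions must hold, so overall power is below the 80% for the margin alone. The rule is also cautious in one case. If the directed-bout gap came from more e-liquid drawn per menthol puff, titration could appear as fewer puffs with equal e-liquid used. The rule would not count that as titration, but the per-puff outcome would help reveal it.

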Tobacco Regulatory Impact of Proposed Research: This proposal will provide additional scientific data to inform regulation of tobacco products by addressing the FDA's Behavior and Addiction scientific interest areas and focus on Africans Americans which represent a vulnerable population. **Behavior** – this proposal seeks to understand the knowledge, attitudes, and behaviors related to use of menthol tobacco products in African Americans. **Addiction** - this application will understand the impact of menthol on nicotine metabolism and dependence in individuals who smoke. **Vulnerable population** - this application could aid in reducing tobacco-related health burdens in African Americans which would benefit overall public health.

The scientific premise for this proposal is to address critical gaps in menthol flavor research by evaluating the impact of menthol and NMR on nicotine pharmacokinetics and subjective in e-cigarettes among African Americans who smoke.

4. **Research Plan:** Summarize the study design and research procedures using non-technical language that can be readily understood by someone outside the discipline. Be sure to distinguish between standard of care vs. research procedures when applicable, and include any flowcharts of visits specifying their individual times and lengths. Describe the setting in which the research will take place.

TCORS menthol pilot study

Uses:

Suorin iShare e-cigarette

DuraSmoke® brand Tobacco Virginia e-liquid, 36 mg/mL nicotine (salt equivalent)

AmericaneLiquid® brand Tobacco-Menthol e-liquid, 36 mg/mL nicotine

DuraSmoke® brand Tobacco Menthol e-liquid, 36 mg/mL nicotine (salt equivalent)

AmericaneLiquid® brand Tobacco-Virginia e-liquid, 36 mg/mL nicotine

This is a double-blind study. Subjects will be blinded to the form of nicotine (salt vs freebase) and the flavor (menthol vs tobacco flavor).

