Experimental design: This proposal seeks to elucidate the differences in reward/appeal, harshness/irritation, nicotine delivery, preference and impact of menthol flavor (compared to control tobacco flavor) between nicotine salt vs free base nicotine e-liquids. Thirty adult menthol smokers (15 male; 15 female) will participate in a double-blind, randomized, cross-over study across three experimental sessions. For the first two sessions, each participant will be randomly assigned to receive nicotine salt or freebase nicotine (both in a concentration of 36mg/ml) on two separate days (see Table 1). Freebase nicotine e-liquid at concentration of 36mg/ml has been used previously in

smokers with no reported adverse effects^{53,54} and this concentration is within range of nicotine concentrations used in nicotine salt e-liquids/e-cigarette pod devices^{55,56}. Following overnight abstinence from combustible tobacco products (CO≤10 ppm), participants will be exposed to the assigned form of nicotine in combination with two flavor conditions (tobacco and menthol) in a counterbalanced randomized order. Each exposure will consist of 2 2-sec puffs and will be separated by a 60-minute washout period (see Table 2).

iSaliva nicotine/ cotinine is an exploratory outcome and nicotine/cotinine levels will be assessed using saliva samples obtained 10 times per session (5 min prior to and 5, 15, 30, 45, and 55 minutes after the onset of puff1, and 5, 15, 30, and 45 minutes after the onset of puff2). Assessing the nicotine/cotinine levels will determine if there are pharmacokinetic differences between nicotine salts vs freebase nicotine. After completing the first two e-cigarette exposure sessions, the same thirty adult menthol smokers (15 female, 15 male) will undergo overnight abstinence from combustible tobacco and nicotine products and participant in a 60-minute choice e-cigarette self-administration session.

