For the safety of participants, we will add plexiglass dividers in the rooms where experimental sessions take place to limit contact between participants and researchers. To limit in-person interactions during experimental sessions, we will give instructions and communicate to participants from another location remotely using a 2-way audio system. Hand sanitizer will be available, and participants will be asked to wear gloves for the duration of the lab session. All devices and areas will be sanitized before and after each participant. These changes have been added to the protocol and consent.

Table 1: Four e-cigarettes conditions that will be used throughout the study.

Nicotine Concentration	Nicotine Condition	Flavor
36mg/ml	salt	tobacco

36mg/ml	salt	menthol
36mg/ml	freebase	tobacco
36mg/ml	freebase	menthol

Table 2: First Two Experimental Sessions Breakdown: Each session participants will be exposed to two separate conditions (see table 3). Below is an example of one session.

• Assessments • Saliva collection (1 sample) • CO	1 st Directed Puff (e-cig condition from table 3)	Nicotine washout period • Assessments • Saliva collection (5 samples)	2 nd Directed puff (a different e-cig condition from table 3)	Nicotine washout period • Assessments • Saliva collection (4 samples)
	5 min	5 min		60 min

Table 3:

Third experimental session design breakdown. 60-minute e-cigarette self-administration

• Weigh e-liquids • CO	Self-administration (ad-lib) [all four of the e-cigarette conditions in Table 3 that participants were exposed to in the Yale TCORS sessions]	• Weigh e-liquids
	5 min	60 min

K01 metabolism study

Uses Juul Device

Menthol eLiquid 59mg/ml (5%) nicotine

Virginia Tobacco eLiquid 59mg/ml (5%) nicotine

Aim 1: Investigate the relationship of menthol flavor (vs tobacco flavor) and NMR on nicotine pharmacokinetics and subjective effects during directed e-cigarette administration.

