subjects in total (43 women, 42 men) we will have 80% power at two-sided alpha level 0.05 to detect a correlation of 0.30 or bigger in absolute value between NMR and the primary study outcomes. For the within subject comparisons of the tobacco and menthol flavor sessions, with 85 individuals we will have 80% power at two-sided alpha level 0.05 to detect a medium effect size (Cohen's $d=0.32$) for the primary study outcomes. This is a cross-over study, so all 85 participants will participate in Aim 1 and Aim 2 of this K01 proposal.

SECTION II: RESEARCH INVOLVING DRUGS, BIOLOGICS, RADIOTRACERS, PLACEBOS AND DEVICES

If this section (or one of its parts, A or B) is not applicable, check off N/A and delete the rest of the section.

A. RADIOTRACERS N/A

1. Name of the radiotracer: *Write here*
2. Is the radiotracer FDA approved? YES NO

If NO, an FDA issued IND is required for the investigational use unless RDRC assumes oversight.

B. DRUGS/BIOLOGICS N/A (IND not applicable; ITP assessed)

TCORS Menthol Pilot Study

The Suorin iShare™ and available e-liquids will be used for this study. The Suorin iShare™ is a refillable pod system e-cigarette device composed of a battery without voltage control and a refillable pod that contains the e-liquid, mouthpiece and coil. It is among one of the pod e-cigarette devices that are used widely^{57,58}. We have received an ITP from the FDA to use this e-cigarette device.

The following e-liquids will be purchased from e-liquid from American eLiquid Store:

- 1) DuraSmoke® Tobacco Menthol eLiquid 36mg/ml
- 2) Tobacco - Menthol eLiquid AmericaneLiquid® 36mg/ml
- 3) DuraSmoke® Tobacco Virginia eLiquid 36mg/ml
- 4) Tobacco - Virginia Flue Cured eLiquid AmericaneLiquid® 36mg/ml

We have received documentation from the American eLiquid Store stating that the above e-liquids were on the market prior to August 2016 so we do not need an ITP for these e-liquids.

K01 Metabolism Study

The JUUL™ and JUULpods™[5%(59mg/ml)] will be used for this study. The JUUL™ is one of the most widely used pod e-cigarette devices^{57,58}. We do not need an ITP from the FDA to use this e-cigarette device and products as they predate the enforcement compliance date.

The following JUULpods will be purchased:

- 1) Menthol eLiquid 59mg/ml (5%)nicotine

2)VirginiaTobacco eLiquid 59mg/ml (5%)nicotine

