4. What will be done with the data when the research is completed? Are there plans to destroy the identifiable data? If yes, describe how, by whom and when identifiers will be destroyed. If no, describe how the data and/or identifiers will be secured. The data will be stored in a locked room for 7 years after the final data is collected. After this point, the Data Manager and Principal Investigator will oversee the process in which data is destroyed or de-identified.
5. If appropriate, has a Certificate of Confidentiality been obtained? A certificate will automatically be applied with the federal funding.

SECTION V: POTENTIAL BENEFITS

Potential Benefits: Identify any benefits that may be reasonably expected to result from the research, either to the subject(s) or to society at large. (Payment of subjects is not considered a benefit in this context of the risk benefit assessment.)

TCORS Menthol Pilot Study

This study will provide preliminary data to the FDA to understand the reward/appeal of freebase vs. the salt form of nicotine when provided in pod e-cigarette devices to adult menthol smokers. This preliminary evidence may provide some clues about which form of nicotine (salt vs freebase) may be more acceptable to help adult menthol smokers transition to e-cigarettes for harm-reduction.

K01 Metabolism Study

There are no direct benefits to the participants. We expect that the results of the study will benefit science and address critical gaps in e-cigarette research by evaluating the impact of nicotine metabolism ratio on pharmacokinetics and subjective effects of menthol in e-cigarettes among African Americans who smoke. The outcomes of the project will provide the FDA with new information to

further develop the knowledge base in understanding menthol flavor and its impact on nicotine dependence.

SECTION VI: RESEARCH ALTERNATIVES AND ECONOMIC CONSIDERATIONS

1. **Alternatives:** What other alternatives are available to the study subjects outside of the research? This is not a treatment study and the alternative is to not participate.
2. **Payments for Participation (Economic Considerations):** Describe any payments that will be made to subjects, the amount and schedule of payments, and the conditions for receiving this compensation.

For TCORS Menthol Pilot

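### In the TCORS pilot each nicotine form comes from a single product line, so the form effect and its interaction with menthol cannot be separated from any difference between the two lines

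*Combined protocol and SAP*

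**What the plan says.** The Research Plan (Section I, item 4) lists four liquids for the TCORS pilot. Two carry a salt label: "DuraSmoke® brand Tobacco Virginia e-liquid, 36 mg/mL nicotine (salt equivalent" and "DuraSmoke® brand Tobacco Menthol e-liquid, 36 mg/mL nicotine (salt equivalent". The other two carry none: "AmericaneLiquid® brand Tobacco-Virginia e-liquid, 36 mg/mL nicotine" and "AmericaneLiquid® brand Tobacco-Menthol e-liquid, 36 mg/mL nicotine". Table 1, captioned "Four e-cigarettes conditions that will be used throughout the study", crosses salt and freebase with tobacco and menthol, so the AmericaneLiquid pair must be the freebase pair. Section II.B lists the same four products.

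The Primary Aim (item 1) is about form. It hypothesizes that menthol reduces irritation more with freebase, and raises reward more with salt. Statistical Considerations (item 13) fits flavor, nicotine form and their interaction within subject, expects a main effect of form on irritation, and has no product term. The experimental design text says of the saliva samples: "Assessing the nicotine/cotinine levels will determine if there are pharmacokinetic differences between nicotine salts vs freebase nicotine". Section V offers the results as preliminary evidence that may give clues about "which form of nicotine (salt vs freebase) may be more acceptable to help adult menthol smokers transition".

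Section II.B.2 says that all liquids come from one store, which makes its own products, and describes a flavor concentrate added to an equal PG/VG base.

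**The concern.** Participants and staff see a blinded, randomized, within-subject comparison of nicotine form. What is actually compared is one commercial line with another. If the lines also differ in flavor concentrate, menthol level or additives, that difference enters the form estimate. Randomization, crossover and blinding do not remove it, because it is a property of the liquids and not of the participants or the order.

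Both primary hypotheses are form-by-menthol interactions, so the main question of the pilot is exposed. The pilot is also meant to supply effect estimates for a larger study, and an estimate that mixes form with product line would carry into that study's planning.

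**Working it through.** TCORS gives no alpha, power, effect size or standard deviation, so there is no stated figure to reproduce. The check is one of identifiability.

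**Step 1. Code the four liquids.** F is form (salt +1, freebase −1), L is line (DuraSmoke +1, AmericaneLiquid −1) and V is flavor (menthol +1, tobacco −1). The liquids come from the Research Plan list, and freebase status from Table 1.

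| Liquid | F | L | V | F×V | L×V |
|---|---|---|---|---|---|
| DuraSmoke tobacco | +1 | +1 | −1 | −1 | −1 |
| DuraSmoke menthol | +1 | +1 | +1 | +1 | +1 |
| AmericaneLiquid tobacco | −1 | −1 | −1 | +1 | +1 |
| AmericaneLiquid menthol | −1 | −1 | +1 | −1 | −1 |

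Columns F and L are identical, and so are F×V and L×V. Both correlations are 1.0.

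**Step 2. Rank.** The planned model (intercept, F, V, F×V) has 4 columns and rank 4. Adding L and L×V gives 6 columns, and the rank stays at 4.

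**Step 3. What each contrast estimates.** Write a cell mean as m + fF + lL + vV + pFV + qLV.

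- Form main effect: the DuraSmoke mean is m + f + l and the AmericaneLiquid mean is m − f − l, so the difference is 2(f + l).
- Menthol minus tobacco within DuraSmoke: 2v + 2p + 2q.
- Menthol minus tobacco within AmericaneLiquid: 2v − 2p − 2q.
- Form-by-flavor, the difference of those two: 4(p + q).

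The alias coefficient is 1.0 in both cases. The line main effect l does not appear in the interaction: a line difference that is the same in both flavors cancels, and only q biases it. Each menthol-minus-tobacco contrast is made inside one line and is a valid comparison of those two products.

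**Step 4. Where the problem lies.** If one line supplied both forms in both flavors (six liquids), or form and line were fully crossed (eight liquids), the rank of the six-column model would be 6. The limit therefore comes from the set of products, not from the number of participants or the model. This step only locates the problem; no change of liquids is proposed.

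**Step 5. Illustration of size.** Assume no true form effect, 30 completers (the target in Section III), a two-sided 0.05 paired t test (29 degrees of freedom), and a pure line difference of d paired standard deviations. The noncentrality is d√30 = 5.477d.

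| Assumed d | Noncentrality | Probability of a significant form result |
|---|---|---|
| 0 | 0 | 0.05 |
| 0.2 | 1.10 | 0.19 |
| 0.3 | 1.64 | 0.36 |
| 0.5 | 2.74 | 0.75 |
| 0.8 | 4.38 | 0.99 |

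The values of d and the alpha are assumptions; the documents give none for this pilot.

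**The case against.** The strongest reply is that the two lines may be much the same apart from form. Section II.B.2 gives one manufacturer and one base, and both forms are stated at 36 mg/ml. This stands as far as it goes: taken at face value, it removes supplier and base as explanations. It does not reach flavor concentrate, menthol level or additives, which no text says are matched. The remark there about uniform constituency concerns buying enough of the solutions in advance, and is not a statement that the lines match each other.

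A second reply is that this is a pilot of 30 completers with a hedged benefit statement. The hedge is real. However, the aims, the analysis section and the pharmacokinetic sentence attribute the contrast to form without reservation.

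A reader might infer four stronger things that the documents do not support:

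- *That the form results simply are brand effects.* No line difference is shown to exist.
- *That a menthol-content difference would by itself produce the hypothesized pattern.* If menthol acts monotonically (an assumption), more menthol in the AmericaneLiquid line favors the irritation hypothesis and works against the reward hypothesis; more in DuraSmoke does the reverse.
- *That the nicotine content differs.* The salt-equivalent label appears for one line only and is not defined, but equal nominal strength is stated repeatedly; only verification is absent.
- *That the tobacco controls differ.* Section II.B gives "Tobacco - Virginia Flue Cured eLiquid AmericaneLiquid® 36mg/ml", but the Research Plan calls the same AmericaneLiquid product plain Virginia, so the name is weak evidence.

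**Conclusion.** The point holds as a limit on what can be concluded. Aliasing of form with product line, and of form-by-flavor with line-by-flavor, is complete and does not shrink with more participants. It rests on the two product lists and on reading AmericaneLiquid as freebase by elimination.

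The size and direction of any bias are unknown. It is zero for the form main effect if the lines differ only in form, and zero for the interaction if their menthol-minus-tobacco formulations match. Neither condition is documented. The within-line flavor contrasts stand, as does the K01 study, which takes both flavors from one product line.

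**What to change.** Without changing any liquid:

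1. In the Primary Aim, the pharmacokinetic statement in the experimental design, Statistical Considerations and Section V, define the factor as DuraSmoke salt versus AmericaneLiquid freebase.
2. Limit conclusions on form and form-by-flavor, and the effect estimates passed to the larger study, to these products. State that nicotine form and product line are inseparable in this design.
3. Where feasible, report manufacturer composition data, or a one-time measurement of nicotine and menthol in the bulk-purchased liquids. This would inform interpretation but not remove the confounding, since other additives would remain unmeasured.

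Items 1 and 2 cost protocol wording and a narrower claim. The cost of item 3 is uncertain: the protocol uses LC/MS laboratories for saliva and plasma nicotine, but does not say that they can assay e-liquids or menthol. Manufacturer data would serve if they cannot.
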